5.4 Dose Limiting Toxicity

5.4.1 DLT evaluation

Toxicities will be assessed according to the NCI Common Terminology Criteria for Adverse Events (CTCAE) version 4.03. A DLT will be defined as any of the following events (described below in 5.4.2), which are attributable to protocol treatment, occurring during the DLT window. The DLT window is defined as the first 28 days of therapy (or completion of 1 cycle of therapy). Any exclusions from these are described in 5.4.3.

5.4.2 DLT definitions

DLT will be defined as the occurrence of any of the following felt to be related to study treatment during Cycle 1:

5.4.2.1 Grade 3 or higher non-hematologic toxicity (see exceptions below in 5.4.3).

5.4.2.2 Grade 4 thrombocytopenia or anemia.

5.4.2.3 Grade 4 neutropenia or Grade 3 febrile neutropenia associated with temperature $> 38^{\circ}\text{C}$.

5.4.2.4 Inability to complete Cycle 1 due to toxicity related to study drug.

5.4.2.5 Delay in administration of scheduled doses of study drug greater than 2 weeks due to *drug related* toxicity of any grade.

5.4.3 DLT exclusions

5.4.3.1 Fatigue, nausea, and/or vomiting (any grade) will NOT be

considered DLTs.

- 5.4.3.2 Lymphopenia not associated with active infection or clinical disease will NOT be considered a DLT.
- 5.4.3.3 Any grade non-hematologic toxicity will NOT be considered a DLT unless continued despite maximum supportive care beyond the 2 week delay allowed in section 5.4.2.5. (see 5.5.8).
- 5.4.3.4 Grade 3 or higher non-hematologic toxicity will be considered a DLT EXCEPT in cases where the event existed at baseline. In these cases, toxicity needs to increase in severity by 2 grades per CTCAE v. 4.03 before it is considered a DLT.

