5.3.2 Dose escalation rules

If a DLT is encountered, the following rules in the table below will be applied (refer to Section 5.4.2 for definitions of DLT). All patients on a given cohort must complete at least 28 days of treatment, and toxicity data must be available for review in order to determine whether accrual should proceed to the next cohort. All toxicity data will be reviewed and dose level changes approved by the DMC prior to enrolling patients to subsequent cohorts.

Table 2: Phase I Dose Escalation Rules

# of Patients with DLT at a Given Cohort Level	Escalation Decision Rules
0 out of 3	Dose escalate to the next higher cohort level.
≥ 2 out of 3	Dose escalation will be stopped. This dose level will be declared the maximum administered dose (MAD). The next lower cohort will be expanded to 6 patients. If no DLTs are observed, an intermediate dose level between this dose and the MAD dose may be considered. The DMC must approve the creation of this intermediate dose level, and the protocol will be amended accordingly.
1 out of 3	Enter 3 more patients at this dose level. If 0 of these 3 patients experience a DLT, proceed to the next dose level.

	If 1 or more of these 3 patients experience a DLT, then dose escalation is stopped and this will be declared the MAD.
≤ 1 out of 6 at the highest dose level below the MAD	This is the MTD and the recommended phase II dose (RP2D).

If ≥ 2 patients in cohort Level -4 demonstrate DLT, the study will close. If 0 out of 3 patients in cohort Level 2 demonstrate DLT, an additional 3 patients will be enrolled at this level. If ≤ 1 out of 6 patients in cohort Level 2 demonstrate DLT, this will be considered the MTD and the RP2D without further dose escalation. A dose level must have 6 evaluable patients to be defined as the MTD.

(Note: The MTD has been identified at dose level -2 (75 mg/m² per day p.o. days 1-7 and 15-21 of Temozolomide and 400 mg per day p.o. days 1-28 of Pazopanib. As of 12.15.15, all patients moving forward will be treated at this dose.)

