5.5.8 Electrolyte Supplementation

Electrolytes should be repleted according to standard institutional protocols.

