5.7.2 Treatment rules for toxicity for phase I AFTER the DLT period

Protocol therapy will be delayed, dose-reduced, or discontinued based upon the most severe toxicity encountered in the previous cycle and/or laboratory parameters on the scheduled day of treatment. For *treatment-related* delays in protocol therapy, the longest permitted interval of treatment interruption is 28 days to remain on study. For *non-treatment-related* delays, the maximum permitted interval is 8 weeks to remain on study. General principles of toxicity management are as follows:

- 5.7.2.1** Temozolomide and pazopanib will be dose-adjusted according to attribution of toxicity. In equivocal cases, the decision may be made by treating investigator with approval from the DMC.
- 5.7.2.2** Individual dose modifications will be made according to the system showing greatest degree of toxicity using NCI CTCAE version 4.03.
- 5.7.2.3** Asymptomatic changes in laboratory values require dose modification only if assessed to be treatment-related, clinically relevant, and represent a change of ≥ 2 grades from baseline.
- 5.7.2.4** If toxicity occurs, supportive care medications should be applied to ameliorate signs and symptoms (refer to Section 5.5) before toxicity grade is determined.
- 5.7.2.5** A patient will be removed from protocol therapy if either of the two study drugs is discontinued.
 - 5.7.2.5.1** Temozolomide will be discontinued if it is not tolerated at a dose of 50 mg/m² daily.
 - 5.7.2.5.2** Pazopanib will be discontinued if it is not tolerated at a dose of 200 mg daily.
- 5.7.2.6** A patient will be removed from protocol therapy if treatment with either of the two study drugs is held for toxicity for longer than 28 days (1 cycle).
- 5.7.2.7** Once a dose has been reduced for toxicity, it should not be re-escalated.
- 5.7.2.8** In obese patients, all dosing is to be determined by the patient's actual body weight.
- 5.7.2.9** If there is more than one indication for dose modification, use the more strict dose modification (i.e. modify according to the most severe toxicity).

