5.7.4.2 Pazopanib dose modifications

There will be no dose modifications of pazopanib for hematologic toxicity of any grade. There will be no dose modifications for grade 1 or 2 non-hematologic toxicities. For grade 3 and/or 4 non-hematologic toxicities, please see Table 7 below.

Table 7: Summary of Hematologic & Non-Hematologic Dose Modifications for Pazopanib

Toxicity	Grade (NCI CTCAE v 4.03)	Pazopanib (PAZ) Adjustment
GASTROINTESTINAL (EXCLUDING HEPATIC DYSFUNCTION)		
Nausea/vomiting, constipation, or mucositis (despite optimal supportive care)	Grade 1	No change
	Grade 2	No change
	Grade 3	Hold PAZ and monitor until \leq grade 2, then decrease 1 level
	Grade 4	Hold PAZ and monitor until \leq grade 2, then decrease 1 level
Diarrhea (despite optimal supportive care)	Grade 1	No change
	Grade 2	No change
	Grade 3	Hold PAZ and monitor until \leq grade 2, then decrease 1 level
	Grade 4	Hold PAZ and monitor until \leq grade 2, then decrease 1 level
CARDIOVASCULAR AND VASCULAR		
Hypertension	Scenario A: Asymptomatic and persistent SBP of \geq 140 and $<$ 170 mmHg, or DBP \geq 90 and $<$ 110 mmHg, or a clinically significant increase in DBP of 20 mmHg (but still below 110 mmHg)	
 1. Continue PAZ at the current dose. 2. Adjust current or initiate new antihypertensive medication(s). 3. Titrate antihypertensive medication(s) during next 2 weeks as indicated to achieve well-controlled BP. If BP is not well-controlled within 2 weeks, consider referral to a specialist and go to Scenario B.
	Scenario B: Asymptomatic SBP \geq 170 mm Hg or DBP \geq 110 mmHg, or failure to achieve well-controlled BP within 2 weeks under Scenario A.	
 1. Consider reducing or interrupting PAZ, as clinically indicated. 2. Adjust current or initiate new antihypertensive medication(s). 3. Titrate antihypertensive medication(s) during next 2 weeks as indicated to achieve well-controlled BP. 4. Once BP is well-controlled, restart PAZ at 1 dose level (200 mg) lower if PAZ was interrupted.

Toxicity	Grade (NCI CTCAE v 4.03)	Pazopanib (PAZ) Adjustment

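### Items 5.4.3.3 and 5.4.3.4 score the same short-lived Grade 3 or higher non-hematologic toxicity in opposite ways, so the rules do not fix the DLT count behind the MTD

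*Combined protocol and SAP*

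**What the plan says.** All of the following is in the combined protocol and SAP.

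- **5.4.1** sets the DLT window at the first 28 days and sends the reader to 5.4.3 for exclusions.
- **5.4.2.1** lists as a DLT "Grade 3 or higher non-hematologic toxicity (see exceptions below in 5.4.3"). It therefore yields to whatever 5.4.3 excludes.
- **5.4.3.1** removes fatigue, nausea and vomiting.
- **5.4.3.3** states "Any grade non-hematologic toxicity will NOT be considered a DLT unless continued despite maximum supportive care beyond the 2 week delay", with a pointer to 5.5.8.
- **5.4.3.4** states "Grade 3 or higher non-hematologic toxicity will be considered a DLT EXCEPT in cases where the event existed at baseline"; for a baseline event, a two-grade worsening is required.
- **5.4.2.4** separately counts "Inability to complete Cycle 1 due to toxicity related to study drug", and 5.4.2.5 counts dose delays of more than two weeks for drug-related toxicity.
- **5.3.2**, Table 2 and the text below it, defines the MTD as the highest level below the maximum administered dose with at most 1 DLT in 6, and adds: "A dose level must have 6 evaluable patients to be defined as the MTD".
- **1.5.6** reports 18 phase I patients treated and the MTD at Level -2 (temozolomide 75 mg/m², pazopanib 400 mg), the dose for all patients from 12.15.15. It gives no DLT counts.

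**The concern.** Items 5.4.3.3 and 5.4.3.4 sit next to each other, cover the same class of event and give opposite answers. The deferral in 5.4.2.1 does not help, because it points to the section that contains both. For a severe non-hematologic toxicity that settles quickly, whether a DLT is recorded depends on which line the assessor follows.

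The DLT count is the only input to Table 2, and Table 2 decides the phase I primary endpoint. The resulting dose is also the one every phase II patient receives. If the rule allows two counts from the same Cycle 1 records, a reader cannot confirm that Level -2 met its criterion without knowing which item was applied.

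**Working it through.** The plan gives no figure to reproduce, so the check sets the rules side by side and then looks at the margin in the MTD criterion.

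**Step 1. Which events are in dispute.** Take a related Grade 3 or higher non-hematologic event in Cycle 1, not present at baseline, and not fatigue, nausea or vomiting.

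| Course of the event | Under 5.4.3.3 | Under 5.4.3.4 |
|---|---|---|
| Resolves within 2 weeks, Cycle 1 completed | Not a DLT | DLT |
| Continues past the 2-week delay despite supportive care | DLT | DLT |
| Stops Cycle 1 | DLT through 5.4.2.4, unless 5.4.3.3 is read to override it | DLT |

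Only the first row is clearly in dispute.

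**Step 2. A clean example.** Grade 3 diarrhea begins in Cycle 1, is treated with loperamide (5.5.1), resolves in 5 days, and no dose is held.

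- Table 7 calls for "Hold PAZ and monitor until" recovery only when diarrhea is Grade 3 despite optimal supportive care, so a hold need not occur.
- 5.4.2.4 does not apply, because Cycle 1 is completed.
- 5.4.2.5 does not apply, because there is no delay.
- 5.4.3.4 scores a DLT; 5.4.3.3 scores none.

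**Step 3. Whether other text settles it.**

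- 5.5.8, the pointer in 5.4.3.3, reads "Electrolytes should be repleted according to standard institutional protocols". That hints at a clause meant for electrolytes, but the clause itself is not so limited.
- 5.7.2.4 has supportive care applied before the grade is fixed, which might have softened the example. Its parent section is headed "Treatment rules for toxicity for phase I AFTER the DLT period", so it does not govern Cycle 1.
- Appendix V, used only for timing, places the present 5.4.3.3 and 5.4.3.4 in the same amendment (Amendment 5, April 15, 2015). Neither supersedes the other, and both predate 12.15.15.

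**Step 4. The window.** The window is 28 days, and 28 - 14 = 14. An event starting after about Day 14 cannot be seen to last more than 2 weeks inside it. Read literally, 5.4.3.3 would exempt most events arising late in Cycle 1.

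**Step 5. The margin.** The criterion is at most 1 in 6. Consider patients with a disputed event who are not already counted for another DLT.

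- 1/6 plus one such patient gives 2/6: Level -2 no longer qualifies.
- 0/6 plus one gives 1/6: it still qualifies.
- 0/6 plus two gives 2/6: it no longer qualifies.

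If Level -2 was scored under 5.4.3.4, moving to 5.4.3.3 can only lower its count, so it would still qualify.

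**Step 6. Illustration on assumed rates only.** The documents give no DLT rates. Let h be the per-patient chance of an undisputed DLT and q that of a disputed event, taken as independent. Under 5.4.3.3, p = h. Under 5.4.3.4, p = 1 - (1 - h)(1 - q). The chance of at most 1 in 6 is (1 - p)^6 + 6p(1 - p)^5. Assume h = 0.15.

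| Assumed q | p under 5.4.3.4 | Chance of at most 1/6 under 5.4.3.4 | Under 5.4.3.3 (p = 0.15) |
|---|---|---|---|
| 0.05 | 1 - 0.85 × 0.95 = 0.1925 | 0.67 | 0.78 |
| 0.10 | 1 - 0.85 × 0.90 = 0.235 | 0.57 | 0.78 |
| 0.17 | 1 - 0.85 × 0.83 = 0.2945 | 0.43 | 0.78 |

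This shows how sensitive the rule is. It does not estimate what happened in this trial.

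**The case against.** The best defence is that 5.4.3.3 was meant narrowly. Its pointer leads to electrolyte supplementation, and the wording it replaced, as listed in Appendix V, concerned metabolic abnormalities. On that reading 5.4.3.4 governs everything else and most of the conflict disappears. This is plausible, but the operative words cover every non-hematologic toxicity, and an assessor following them would not be misapplying the protocol.

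Second, 5.3.2 has the DMC review all toxicity data and approve each change of dose level, so one body oversaw scoring across sites. That makes inconsistent scoring less likely. It does not say which item that body used, and Table 2 still acts on a count.

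Third, a protocol is not where DLT results are reported, and phase I dose finding is over. Both are true. The absence of counts in 1.5.6 is therefore not itself a fault, and the remedy belongs in the phase I report. DLT scoring also has no role in the phase II response analysis.

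A reader might infer that 5.4.2.1 itself contradicts 5.4.3.3. It does not, because it expressly gives way to 5.4.3. A reader might also infer that Level -1 was rejected on events that 5.4.3.3 would not count. The documents do not date any cohort against Amendment 5. If Level -1 was scored earlier, these two items were not both in force.

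**Conclusion.** The contradiction between 5.4.3.3 and 5.4.3.4 stands and should be resolved in the report. It covers new, related Grade 3 or higher non-hematologic events in Cycle 1, other than fatigue, nausea or vomiting, that resolve within 2 weeks without stopping the cycle. Because the criterion is at most 1 in 6, a single rescored patient is enough to change whether Level -2 qualifies, if its count stands at 1.

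It would be tempting to conclude that the declared MTD is wrong or the phase II dose unsafe. The documents do not support that. They give no DLT counts, no event types and no statement of the rule used; affected patients may number zero, and the narrow reading of 5.4.3.3 may have been applied throughout. What is established is that the written rule does not determine the count. The clash follows from the current text alone. The probabilities in the illustration rest wholly on assumed rates and independence, and the conclusion does not depend on them.

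**What to change.** Leave the DLT window and the declared MTD as they are.

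1. In the phase I report, state which item governed Grade 3 or higher non-hematologic toxicity at each dose level, and from what date. Note if Level -1 was scored under wording that preceded Amendment 5.
2. From Cycle 1 records already held, give the Level -2 DLT count under both readings. Do the same for Level -1 if it was scored under the current wording. Keep the count on which the MTD was declared as the reported result and label the other a sensitivity count.
3. If Level -2 shows 2 or more of 6 under 5.4.3.4, notify the DMC while phase II patients are being treated at that dose.

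The cost is a short statement in the report and a re-read of Cycle 1 toxicity records for at most 18 patients. No cohort or dose changes, and no new data are needed. The drawback is that the second count is post hoc and may be less favourable.

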3.2 Inclusion Criteria

3.2.1 Patients must have histologically confirmed well –differentiated islet cell carcinoma (PNET) not amenable to surgical resection.

3.2.2 Patients must be age 18 years or older.

- 3.2.3** Patients may have had 0-4 prior therapies.
 - 3.2.3.1** Prior chemoembolization or local ablative therapies are permitted if completed \geq 6 weeks prior to study enrollment.
 - 3.2.3.2** Prior temozolomide is permitted.
- 3.2.4** Patients must have an ECOG performance status \leq 2 (refer to Appendix I).
- 3.2.5** Patients must have a life expectancy $>$ 3 months.
- 3.2.6** Patients must have radiographically measurable disease as defined by RECIST version 1.1 criteria.
- 3.2.7** Patients' baseline blood pressure must be adequately controlled with or without antihypertensive medications prior to enrollment (systolic $<$ 140 mmHg, diastolic $<$ 90 mmHg).
- 3.2.8** Patients must have LVEF \geq 50 as measured by echocardiogram or MUGA.
- 3.2.9** Patients must have adequate baseline organ and marrow function as defined below:
 - 3.2.9.1** Absolute neutrophil count (ANC) \geq 1,500/ μ L
 - 3.2.9.2** Platelets \geq 100,000/ μ L
 - 3.2.9.3** Hemoglobin \geq 9.0 g/dL
 - 3.2.9.4** Total bilirubin \leq 2 mg/dL or \leq 1.5 times upper limit of normal (ULN)
 - 3.2.9.5** AST (SGOT) and ALT (SGPT) \leq 2.5 times ULN
 - 3.2.9.6** INR \leq 1.2 times ULN. Subjects receiving anticoagulant therapy are eligible if their INR is stable and within the recommended range for the desired level of anticoagulation.
 - 3.2.9.7** Activated partial thromboplastin time (aPTT) \leq 1.2 x ULN
 - 3.2.9.8** Albumin \geq 2.8 g/dL
 - 3.2.9.9** Serum creatinine \leq 1.5 times ULN OR if serum creatinine \geq 1.5 mg/dL, calculated creatinine clearance \geq 30 mL/min
 - 3.2.9.10** Urine protein to creatinine ratio $<$ 1 OR 24-hour urine protein $<$ 1 g
- 3.2.10** Patients must be able to tolerate oral medications.
- 3.2.11** Females of child-bearing potential must have a negative pregnancy test within 14 days of study enrollment and must agree to use an effective method of birth control during treatment and for three months after receiving their last dose of study drug. Males must agree to use an effective method of birth control during treatment and for three months after receiving their last dose of study drug. All patients must notify treating provider immediately if any suspicion of pregnancy or conception.

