5.7.4.1 Temozolomide dose modifications

Please refer to Table 6 below for a summary of dose modifications for temozolomide for both hematologic and non-hematologic toxicities. Toxicities that are judged to be unrelated to study drug will not require dose modifications.

Table 6: Summary of Hematologic & Non-Hematologic Dose Modifications for Temozolomide

Toxicity	Grade (NCI CTCAE v 4.03)	Temozolomide (TMZ) Adjustment
HEMATOLOGIC		
Neutropenia	Grade 1 ANC 1500 to < 2000/mm ³	No change
	Grade 2 ANC 1000 to < 1500/mm ³	No change

Toxicity	Grade (NCI CTCAE v 4.03)	Temozolamide (TMZ) Adjustment
	Grade 3 ANC 500 to < 1000/mm ³	Hold TMZ, repeat CBC weekly until \leq grade 2, then decrease 1 level
	Grade 4 ANC < 500/mm ³	Hold TMZ, repeat CBC weekly until \leq grade 2, then decrease 1 level
Lymphopenia	Any Grade	No dose reductions
Thrombocytopenia	Grade 1 Plts 75,000 to < LLL/mm ³	No change
	Grade 2 Plts 50,000 to 75,000/mm ³	No change
	Grade 3 Plts 25,000 to < 50,000/mm ³	Hold TMZ, repeat CBC weekly until \leq grade 2, then decrease 1 level
	Grade 4 Plts < 25,000/mm ³	Hold TMZ, repeat CBC weekly until \leq grade 2, then decrease 1 level
Anemia	Any Grade	No dose reductions or delays will be performed for anemia; transfusions and/or growth factor support may be used at the discretion of the investigator
ALL OTHER NON-HEMATOLOGIC TOXICITY		
Other toxicity (despite optimal care)	Grade 1	No change
	Grade 2	No change
	Grade 3	Hold TMZ until \leq grade 2, then decrease 1 level
	Grade 4	Discontinuation of therapy and removal from study

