10.2.2 Severity of AEs

All non-hematologic adverse events will be graded according to the NCI Common Terminology Criteria for Adverse Events (CTCAE) version 4.03. The CTCAE v4 is available at

<http://ctep.cancer.gov/reporting/ctc.html>

If no CTCAE grading is available, the severity of an AE is graded as follows:

- 10.2.2.1 Mild (grade 1):** the event causes discomfort without disruption of normal daily activities.
- 10.2.2.2 Moderate (grade 2):** the event causes discomfort that affects normal daily activities.
- 10.2.2.3 Severe (grade 3):** the event makes the patient unable to perform normal daily activities or significantly affects his/her clinical status.
- 10.2.2.4 Life-threatening (grade 4):** the patient was at risk of death at the time of the event.
- 10.2.2.5 Fatal (grade 5):** the event caused death.

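### By the grade criterion, a related non-hematologic event that worsens from grade 3 at baseline to grade 4 is not a DLT, and the remaining DLT clauses do not give such an event one clear verdict

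*Combined protocol and SAP*

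**What the plan says.** Section 5.4.2 lists five alternative DLT criteria for treatment-related events in Cycle 1. The grade criterion for non-hematologic events, 5.4.2.1, reads "Grade 3 or higher non-hematologic toxicity (see exceptions below in 5.4.3". Two others carry no grade or baseline condition: 5.4.2.4, "Inability to complete Cycle 1 due to toxicity related to study drug", and 5.4.2.5, a dosing delay of more than 2 weeks for related toxicity of whatever grade.

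Section 5.4.3.4 sets the baseline exception: "Grade 3 or higher non-hematologic toxicity will be considered a DLT EXCEPT in cases where the event existed at baseline". It continues: "In these cases, toxicity needs to increase in severity by 2 grades per CTCAE v. 4.03 before it is considered a DLT". It puts no ceiling on the baseline grade and makes no separate provision for reaching grade 4.

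Section 5.4.3.3 excludes non-hematologic toxicity of every grade unless it persists, despite full supportive care, past the 2-week delay. Section 5.4.1 refers the reader to 5.4.3 for exclusions from the listed events, without saying which items they reach.

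The severity scale printed in Section 10.2.2, for events without a CTCAE grade, describes grade 4 as "the patient was at risk of death at the time of the event" and grade 5 as "the event caused death". For grade 4 non-hematologic toxicity, Table 6 (temozolomide) says "Discontinuation of therapy and removal from study". Table 7 stops pazopanib for grade 4 toxicity in its residual category, but for nausea/vomiting, constipation, mucositis, diarrhea and hand-foot syndrome it holds the drug and then reduces it.

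**The concern.** The DLT count is the phase I primary endpoint, and by Table 2 it decides the MTD, which is the phase II dose. A shift-from-baseline rule on a scale that stops at 5 runs out of room at high baseline grades. The events it releases from the grade criterion include ones the protocol itself calls life-threatening. An exception of this kind can only remove DLTs, never add them, so any effect on the declared MTD is upward. If the neighbouring clauses also disagree, two assessors could score the same patient differently, and the reported count cannot be reproduced from the protocol.

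**Working it through.** No sample size, power or error rate rests on 5.4.3.4, so there is no stated figure to reproduce. The check is grade arithmetic followed by a side-by-side reading.

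**1. Grade arithmetic.** Grade required = baseline grade + 2 (5.4.3.4). I take CTCAE 4.03 to run from 1 to 5 with the meanings printed in Section 10.2.2.

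| Baseline grade | Grade required | Worsening to grade 3 or above not counted by grade |
|---|---|---|
| 1 | 1 + 2 = 3 | none |
| 2 | 2 + 2 = 4 | to grade 3 |
| 3 | 3 + 2 = 5 | to grade 4 |
| 4 | 4 + 2 = 6, which does not exist | to grade 5 |

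**2. Do the other routes catch a related 3-to-4 worsening?**
- If treatment stops in Cycle 1, 5.4.2.4 applies. Table 6 and the residual row of Table 7, if applied in Cycle 1, would lead there.
- If dosing is delayed more than 2 weeks, 5.4.2.5 applies.
- Take grade 4 diarrhea attributed to pazopanib. Table 7 holds and reduces, and Section 5.7.4 treats held doses as omitted rather than postponed, so the cycle runs on. With a hold under 2 weeks, neither route is clearly met.
- Only 5.4.2.1 refers to the exceptions in 5.4.3, which suggests that 5.4.2.4 and 5.4.2.5 stand unaffected. The general pointer in 5.4.1 can also be read to cover all five criteria. The text does not settle this.

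**3. Section 5.4.3.3 against 5.4.2.1 and 5.4.3.4.** Take a related grade 4 non-hematologic event, absent at baseline, that resolves within 2 weeks. It is a DLT under 5.4.2.1 and the opening of 5.4.3.4, and not a DLT under 5.4.3.3. Section 5.4.3.3 cross-refers to 5.5.8 (electrolytes), but its wording is not limited to electrolytes.

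**4. Who could be affected?** Sections 3.2 and 3.3 cap AST/ALT, bilirubin, creatinine, INR, aPTT, albumin, urine protein, blood pressure and QTc. They set no limit on alkaline phosphatase, electrolytes or diarrhea, and do not generally bar a baseline grade 3 event. No figure for such events is given.

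**5. What one restored event would do at Level -2.** The MTD rule is at most 1 DLT in 6.
- Counted total 0: 0 + 1 = 1 of 6, and the MTD stands.
- Counted total 1: 1 + 1 = 2 of 6, and the rule fails.

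The documents do not say which applies.

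**6. Illustration of scale, by assumption only.** Let p be the true DLT probability, f the fraction uncounted, and q = p(1 − f). Then P(at most 1 of 6) = (1 − q)^6 + 6q(1 − q)^5. For p = 0.33 and f = 10%, q = 0.297 and the sum is 0.121 + 0.306 = 0.427.

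| p | f = 0 | f = 5% | f = 10% | f = 20% |
|---|---|---|---|---|
| 0.33 | 0.358 | 0.391 | 0.427 | 0.501 |
| 0.20 | 0.655 | 0.680 | 0.704 | 0.753 |

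Nothing in the documents supports a particular value of p or f.

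**The case against.** A reader might infer that an event at grade 3 at baseline becomes a DLT only if it kills the patient, and that a worsening to grade 4 is scored as tolerated. The documents do not support that. Any one of the five criteria suffices, and 5.4.2.4 and 5.4.2.5 have no baseline condition. The tables would often force the first of these. Section 5.3.2 also has the DMC review all toxicity data, not only DLTs, before a dose level changes. This part of the objection stands, and it limits the point to the grade criterion and to the unclear link between clauses.

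The other side can add that a 2-grade shift is used elsewhere in the protocol (5.7.2.3, for asymptomatic laboratory changes), that eligibility caps and the exclusion of fatigue, nausea and vomiting in 5.4.3.1 shrink the affected set, and that no text shows the exception was ever used. These are fair. The 5.7.2.3 parallel is weak, because that rule concerns asymptomatic findings after the DLT period. It is also tempting to cite 3.2.7, "Patients' baseline blood pressure must be adequately controlled with or without antihypertensive medications prior to enrollment", as a source of high baseline grades, but that would need CTCAE hypertension criteria that the documents do not contain.

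Last, the MTD has been declared and the dose fixed since 12.15.15, so rewording alone changes no pending dose decision. That is true of the wording. It does not remove the value of knowing whether the count behind the phase II dose depends on an exclusion.

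**Conclusion.** The point holds in limited form. By grade alone, a related worsening from baseline grade 3 to grade 4 is not a DLT, and a baseline grade 4 event can never become one. Whether another criterion recovers such an event depends on how treatment was handled and on how 5.4.1 is read. Section 5.4.3.3 contradicts 5.4.2.1 and 5.4.3.4 for short non-hematologic events whatever the baseline.

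The affected set is probably small and cannot be sized from the documents. The direction is certain: the exception can only lower the DLT count. The consequence is not. It would not be sound to conclude that the MTD is too high, since the Level -2 DLT count is unreported and one restored event matters only if the counted total was already 1 of 6. The binomial figures show sensitivity under assumed inputs and are not estimates for this trial. The conclusion assumes that CTCAE 4.03 shares the five-grade scale in Section 10.2.2.

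**What to change.** Reconcile 5.4.1, 5.4.2.1, 5.4.2.4, 5.4.2.5, 5.4.3.3, 5.4.3.4 and Tables 6 and 7 so that each Cycle 1 event has one verdict. State expressly how a baseline event that worsens to grade 4 is scored, and whether the exclusions reach 5.4.2.4 and 5.4.2.5. Which rule should govern is for the investigators and the DMC; none is proposed here.

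For the 18 patients treated in phase I (Section 1.5.6), list every related Cycle 1 event not counted because of 5.4.3.3 or 5.4.3.4, with its baseline and worst grade. Note which DLT definition was in force for each patient: Appendix V records that 5.4.3.4 was added in Amendment 5 (April 2015), eight months before the MTD date, so cohorts may have been scored under different rules. Report the DLT count per dose level, Level -2 in particular, with and without these exclusions.

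Table 10 schedules toxicity assessment at screening and on Days 1, 8, 15 and 22 of Cycle 1, so no new patients or visits are needed. The cost is a clarifying amendment, a small re-tabulation, and a reported DLT count that may be less favourable.
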